**C.1.g. Social Salience measures:** For the purposes of the R21 and the R33 we will use behavioral measures of social preference to assess social salience. The two tasks, a gaze-cuing task and a one-armed bandit task, assess social orienting and social reward, respectively, and both are considered indices of social salience. As noted below, recent work in our laboratory indicates that individuals with schizophrenia are less likely than controls to show a preference for social cues.

**Gaze-cuing task:** To assess social orienting, we will use a gaze-cuing task in which subjects will be asked to indicate the location of a target (the letter X in one of two peripheral boxes) following an uninformative central cue (either social or nonsocial) [46, 47]. The social cue will be a drawing of eyes gazing left or right; the nonsocial cue will be an arrow pointing left or right. On each trial a fixation cross will be presented for 700 ms along with two peripheral boxes (left and right), followed by the cue at the center of the screen for 150 ms. After cue offset, the target will appear and remain on the screen until a response is made. Subjects will be asked to detect the location of the target as quickly and accurately as possible; both accuracy and reaction time will be

recorded. We will use 4 stimulus onset asynchronies (SOAs) between the cue and the target (i.e., SOA of 150, 250, 350, and 700 ms) to examine the time course of social orienting across SZ patients and controls as a function of the SOA. There will be 100 trials for each SOA per type of cue (social or nonsocial); there will also be 40 catch trials with a nondirectional cue to detect and exclude invalid performance. Both social and nonsocial cues are uninformative, meaning that the direction of the cue will be consistent with the target location on half of the trials (congruent condition) and inconsistent on the other half (incongruent condition). The two types of cues will be randomly presented throughout the task. The difference between congruent and incongruent conditions is the cuing effect. The dependent measure typically used is the ratio of social and nonsocial cuing effects: a ratio greater than 1.0 shows preferential orienting towards social cues. This task will take 30 minutes to complete.

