**Pilot data:** We adapted an existing task [46, 47] and collected pilot data with 3 controls and 3 schizophrenia patients who were stable on antipsychotic medication. As expected, controls showed a ratio greater than 1.0, indicating a preferential orienting for social cues. In contrast, patients showed a preference towards nonsocial stimuli (ratio <1.0) (Figure 3).

[figure not shown]
**One-armed bandit task:** To measure reactivity to social vs. nonsocial rewards, we will employ a one-armed bandit task [48, 49]. This task has two blocks with identical trial structures except for the type of reward (i.e., social or nonsocial). The order of the blocks will be counterbalanced across subjects. For the social reward block, we will use color photographs of unfamiliar faces from the NimStim collection [50], showing happy (positive outcome), angry (negative outcome) or neutral (neutral outcome) emotional expressions. For nonsocial reward, we will use: an image of a dollar bill (positive outcome), an image of a dollar bill crossed out (negative outcome), or an image of an empty rectangle (neutral outcome).

For each trial, after a fixation point (500 ms), two slot machines will appear: a “neutral” machine paired either with a “good” slot machine or a “bad” slot machine. A good slot machine has an 80% probability of a positive outcome and a 20% probability of neutral outcome; a bad slot machine has an 80% probability of negative outcome and a 20% probability of neutral outcome; and a neutral machine is always associated with neutral outcome. Subjects will have up to 2.5 seconds to choose the slot machine that will give them the optimal outcome. Then, the reward outcome will be presented for 1.5 s. The main dependent measure will be the total number of trials the subject chooses the machine with the optimal outcome (i.e., a good over a neutral machine; a neutral over a bad machine). Subjects will not be told the reward probabilities of each slot machine and need to learn them over the course of the task. All subjects will receive the same compensation regardless of their performance. This task takes 30 minutes to complete.

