**C.1.h. Data Analysis:** The primary goal of the R21 phase is to determine the dose response curve to RT for mu suppression and pupillary response. Prior to modeling the form of the curves we will obtain descriptive statistics and graphical summaries for the measures of target engagement on placebo, at each of the active doses. We will also plot the within subject change scores and the overall dose-response curve. To formally determine whether there is target engagement we will fit a logistic dose response curve to the data for each of the outcome measures. We assume that the OT dose response curve can be adequately modeled using a 4-parameter model with a lower asymptote, slope, E50 (point of half of maximum response), and upper asymptote as the parameters. However, we will also fit a 5 parameter model that allows for an asymmetry in the acceleration and deceleration of the change slope to determine whether the additional parameter is necessary to represent the empirical dose response curve. Independent of which of the models for the dose

response curve we finally choose we will determine whether there is target engagement by testing whether the upper asymptote is significantly different from zero using a z-test based on the parameter estimate and its standard error. Specifically this test allows us to determine whether there is a measurable change in the outcome variable of interest at the optimum dose of OT (where the upper asymptote is reached) while borrowing strength across all the measurement points. For the secondary aim, examining the relationship between target engagement and social salience we will use multiple linear regression models with the social salience measures as the outcomes and change in pupillary response and mu suppression in response (OT vs placebo) as the predictors, adjusted for OT dose.

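### The only gaze-cuing score defined for Aim 2 is a ratio of two signed reaction-time differences with no rule for a zero or negative denominator; a difference in ms is safer

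*Combined protocol and SAP*

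**What the plan says.** Section C.1.g (Gaze-cuing task) builds the score in two steps. First, "The difference between congruent and incongruent conditions is the cuing effect"; this is computed separately for social cues (eyes) and nonsocial cues (arrows). Then "The dependent measure typically used is the ratio of social and nonsocial cuing effects", with the reading that "a ratio greater than 1.0 shows preferential orienting towards social cues". No other gaze-cuing score is defined. The pilot in the same section ("collected pilot data with 3 controls and 3 schizophrenia patients") is reported on this ratio, and the text gives no means or variances for it.

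Section C.1.h (Data Analysis) handles the secondary aim with "multiple linear regression models with the social salience measures as the outcomes". The predictors are the OT-versus-placebo changes in pupil response and mu suppression, with adjustment for dose. It gives no transformation, robust method or denominator rule. It also leaves open whether the score uses reaction time or accuracy ("both accuracy and reaction time will be" recorded), whether it is pooled over the four SOAs, and whether the outcome is the OT-day value or the OT-placebo change.

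The Specific Aims state that Aim 2 is exploratory and does not enter the Go/No Go decision.

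**The concern.** A cuing effect is a difference of two mean reaction times, so in a single subject at a single visit it can be small, zero or negative. Dividing by it causes two separate problems.

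- **Negative denominator.** The above-1.0 rule gives the opposite answer to the data.
- **Small positive denominator.** The subject stays on the correct side of 1.0, but the ratio becomes very large. Least squares gives such values heavy weight, and a handful can set or mask the slope.

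At stake is Aim 2, the link between target engagement and social salience. Section C.1.g plans the same tasks for the R33, so a null result produced by the scoring could carry over into how the next phase is read.

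**Working it through.** The documents state no power or effect size for Aim 2, so there is no figure to reproduce. The powers in the Power paragraph of C.1.h concern the Aim 1 asymptote.

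**1. The reversal (no assumptions).** Let S and N be the social and nonsocial cuing effects, taken as incongruent minus congruent reaction time. If N > 0, then S/N > 1 exactly when S > N. If N < 0, then S/N > 1 exactly when S < N, so the rule is wrong for every subject with a negative N.

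| S (ms) | N (ms) | S/N | Ratio reads | S − N (ms) | Difference reads |
|---|---|---|---|---|---|
| +15 | −2 | −7.5 | not social | +17 | social |
| −20 | −5 | +4 | social | −15 | not social |
| +15 | +10 | 1.5 | social | +5 | social |
| +15 | +2 | 7.5 | social | +13 | social |

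The last two rows show inflation without reversal: the difference rises 2.6-fold (13/5), and the ratio rises 5-fold (7.5/1.5).

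**2. How often the denominator is at or below zero.**

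Inputs from C.1.g: 100 trials per SOA and cue type, 4 SOAs, half congruent. That is 400 trials per cue type, or 200 against 200 pooled (50 against 50 per SOA).

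Assumed, because the documents do not give them: trial SD 80–150 ms, mean effect 10–40 ms, between-subject SD equal to 30% of the effect.

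- SE of one pooled cuing effect = SD × √(2/200) = SD/10, so 8 to 15 ms.
- P(N ≤ 0) = Φ(−effect / √(SE² + (0.3 × effect)²)).
- Example, SD 100 and effect 15: √(100 + 20.25) = 10.97; 15/10.97 = 1.37; P = 8.6%.

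| Mean effect | SD 80 | SD 100 | SD 150 |
|---|---|---|---|
| 10 ms | 12.1% | 16.9% | 25.7% |
| 15 ms | 5.1% | 8.6% | 16.9% |
| 25 ms | 1.1% | 2.3% | 6.8% |
| 40 ms | 0.3% | 0.5% | 1.9% |

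Scored per SOA, the SE doubles to SD/5 and the range becomes about 2–37%. The chance that at least one of 48 OT-day values is affected is 1 − (1 − p)^48: about 42% at 25 ms and SD 80, and about 13% at 40 ms and SD 80.

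**3. Power in the Aim 2 regression.** The simulation used 48 subjects (6 at each of 8 doses), two engagement predictors plus linear dose (48 − 4 = 44 df), and a two-sided 0.05 test (level assumed). The true social cuing effect on OT rises by half the mean cuing effect per SD of engagement. Noise is as in step 2.

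| Outcome | Setting | Ratio | Difference |
|---|---|---|---|
| OT-placebo change | SD 100, 15 ms | 8% | 69% |
| OT-placebo change | all settings | 5–74% | 18–100% |
| OT-day value | SD 100, 15 ms | 14% | 87% |
| OT-day value | all settings | 6–83% | 31–100% |

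The difference had the higher power in every setting. The top of each ratio range is at 40 ms with SD 80. The low end of the difference for the change (10 ms, SD 150) varied between about 18% and 21% across runs.

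**4. Does the result depend on that model?** In a second set, with effects sized so that the difference has roughly 75–80% power and with trial SD 80 ms, the OT-day comparison of ratio with difference was 10% vs 77% at 10 ms, 43% vs 76% at 30 ms, 61% vs 77% at 40 ms and 73% vs 77% at 60 ms. With the true effect placed on the ratio itself, which should favour the ratio, it was 11% vs 76% at 10 ms, 35% vs 76% at 30 ms and 62% vs 73% at 60 ms. Type I error of the ratio analysis stayed at 4.5–5.9%.

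**The case against.** **The frequency is not documented.** The protocol gives no reaction-time SD, cuing-effect size or denominator distribution. A reader might infer that the denominator is often zero or negative, and the documents do not support that. At 40 ms and SD 80 it happens in about 0.3% of visits. This stands, which is why the result is given as a range.

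**The power loss is conditional.** A reader might also infer that Aim 2 could not be seen with the ratio even if the link were strong. That does not follow: at 40 ms and SD 80 the ratio reaches 74% power for the change and 83% for the OT-day value. This stands too.

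**The wording is descriptive.** C.1.g says what is typically used, whereas for the one-armed bandit task it states what the main measure will be. So the protocol does not strictly bind Aim 2 to the ratio. But it defines no other gaze-cuing score and reports the pilot on this one. If the ratio is not meant, the outcome is undefined, and the same sentence is needed.

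**Other remedies exist, and the difference has limits.** A rank analysis of the ratio change recovers much of the loss in a quiet setting (95% against 36% at 25 ms, SD 80) but less in a noisier one (33% at 15 ms, SD 100). It leaves the reversal in place. The difference itself has low power at the noisy end, and it is not scaled for general slowing. These limits stand but do not favour the ratio.

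**Impact is small.** Aim 2 is exploratory, no power is claimed for it, and the one-armed bandit outcome is a count of optimal choices with no such division. This stands and limits the weight of the point.

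**Conclusion.** The point holds in a limited form. The reversal under a negative nonsocial effect follows from the protocol's own definitions and needs no assumption. Small positive denominators inflate the score but do not reverse it.

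The size of the harm rests on assumed reaction-time values. Under them, the loss of power is severe when cuing effects are small or reaction times noisy. It is modest when effects are large and reaction times quiet (73% against 77% at 60 ms and SD 80 in the second set). The difference did better in every setting examined, including when the true effect was on the ratio.

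The harm is lost power and misread individual subjects, not false positives. It is worth correcting because the change is nearly free. It does not touch Aim 1 or the Go/No Go decision.

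**What to change.** In C.1.g and C.1.h, name one Aim 2 gaze-cuing outcome: the social minus the nonsocial cuing effect in ms. Compute each effect as incongruent minus congruent mean reaction time, pooled over the four SOAs, so that values above 0 mean social preference. State whether the outcome is the OT-day value or the OT-placebo change. Report the ratio only descriptively, from group means.

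Add a sensitivity analysis that divides the difference by the subject's mean reaction time. If the ratio is kept as an outcome after all, it needs a stated denominator rule and a robust analysis.

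Cost: a sentence or two in the plan and one extra analysis, with no new data. The downsides are that results will not be on the scale of earlier ratio reports, and that a raw ms difference does not allow for general slowing, which the sensitivity analysis addresses.

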**Pilot Data:** We adapted an existing one-armed bandit task [48, 51] and piloted it with 4 controls and 7 stable schizophrenia patients on antipsychotic medication (Figure 4). For the social reward condition, the patients chose the optimal outcome much less frequently than the controls did; but the two groups did not differ on the nonsocial reward condition.

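### The one-armed bandit score for Aim 2 is a total with no social-versus-nonsocial contrast and no stated block rule, and the Aim 2 regression has no visit-order term

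*Combined protocol and SAP*

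**What the plan says.** Section C.1.g sets out what the two behavioural tasks are for: "we will use behavioral measures of social preference to assess social salience". Section A.4 defines social salience comparatively, as a bias towards giving cognitive resources to social information, seen as a preference when both kinds of stimulus are present.

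The bandit task is introduced in the same terms: "To measure reactivity to social vs. nonsocial rewards, we will employ a one-armed bandit task". It has a social and a nonsocial block that differ only in the type of reward. The score is then given as "The main dependent measure will be the total number of trials the subject chooses the machine with the optimal outcome", explained by the two machine pairings: "a good over a neutral machine; a neutral over a bad machine". The two blocks are not mentioned in that definition.

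The bandit pilot data in C.1.g are described by condition. On social reward, "For the social reward condition, the patients chose the optimal outcome much less frequently than the controls did"; on nonsocial reward, "the two groups did not differ on the nonsocial reward condition".

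For the other salience task, gaze-cuing, a comparative score is given: "The dependent measure typically used is the ratio of social and nonsocial cuing effects".

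Section C.1.h analyses Aim 2 by multiple linear regression. The salience measures are the outcomes, the OT-versus-placebo changes in pupil response and mu suppression are the predictors, and OT dose is the only adjustment. It does not name the bandit score, say whether that score is an OT-minus-placebo change, or include a term for visit order. Under Specific Aims, Aim 2 is exploratory and plays no part in the Go/No Go decision.

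**The concern.** The task was built to support a comparison, but the only score defined for it is not comparative. If that score enters the Aim 2 regression, a positive association could mean that subjects with more target engagement learned any reward contingency better, social or not. That is a different conclusion from the one Aim 2 is meant to support.

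The definition also leaves several scores open: a pooled total, a social-block total, two separate totals, or a contrast. Choosing among them after the data are seen would weaken an exploratory result that C.1.g intends to carry into the R33, where the same measures are to be used.

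Visit order adds a second problem. Subjects must learn the reward probabilities by playing, and they do so at two challenges a week apart. Practice on the bandit task, and practice or habituation in the physiological responses, are both plausible.

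**Working it through.** The plan states no figure on this point. The power calculation in C.1.h concerns the upper asymptote for mu suppression and pupil response, so there is nothing to reproduce. The check has four steps.

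**1. What the total contains.** Write the social-block score as S = g + s and the nonsocial-block score as N = g + n, where g is general reward learning (taken, for simplicity, to load equally on both blocks) and s and n are specific to the reward type.
- Pooled total: S + N = 2g + s + n.
- Social-block total: S = g + s.
- Contrast: S − N = s − n.

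Only the contrast removes g, so the gap exists on either reading of the total.

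**2. If the blocks were pooled (conditional illustration).** With block SDs σS and σN and between-block correlation r,

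corr(S+N, S−N) = (σS² − σN²) / √[(σS² + σN²)² − 4r²σS²σN²].

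The documents give none of these inputs. The assumed range is σS/σN from 0.67 to 1.5 and r from 0 to 0.7.

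| σS/σN | r = 0 | r = 0.3 | r = 0.5 | r = 0.7 |
|---|---|---|---|---|
| 0.67 | −0.38 | −0.40 | −0.43 | −0.50 |
| 1.0 | 0 | 0 | 0 | 0 |
| 1.5 | 0.39 | 0.40 | 0.43 | 0.50 |

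With equal SDs a pooled total carries no linear information about the contrast. Over the same grid it would still correlate 0.56 to 0.95 with the social-block score, so it would not be empty of social signal.

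**3. What the contrast costs.** Assume equal block variances σ² and an OT effect on the social block only. Here r is the correlation between block *change* scores (OT minus placebo), which need not equal the correlation between raw block scores.
- Var(S) = σ² and Var(S − N) = 2σ²(1 − r).
- Signal-to-noise of S − N relative to S alone = 1/√[2(1 − r)].
- r = 0.3: 1/√1.4 = 0.85. r = 0.5: 1/√1.0 = 1.00. r = 0.7: 1/√0.6 = 1.29.

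The contrast is noisier than the social block alone when r is below 0.5. Adjusting S for N by regression leaves variance σ²(1 − r²), which is 0.91σ², 0.75σ² and 0.51σ² at the same three values. It is therefore never noisier than S alone, but it removes g only in part.

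**4. Visit order.** Let z = +1 if OT is given at the second challenge and −1 if at the first. Write the bandit change as Y = μY + za + eY and a physiological change as X = μX + zb + eX, where a and b are the visit-2-minus-visit-1 shifts. Then

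Cov(X, Y) = ab·Var(z) + Cov(eX, eY),

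with Var(z) = 1 when order is balanced. Without an order term the product ab stays in the association. It is zero only if one of the shifts is zero, and its sign can create or mask a relation. If Y is the contrast, a becomes aS − aN, which vanishes when practice is the same in both blocks. The order term handles what is left.

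**The case against.** The strongest reply is that the plan never says the blocks are added together. The explanation attached to the total names the two machine pairings, which fits a total within each block. The task's stated purpose and the pilot report by condition also point to per-block scoring. This stands. A reader might infer that the plan pools the blocks, so that the score is simply general reward learning and a large, calculable share of the information is lost. The documents do not support that inference. Pooling is not stated, and any percentage loss would further require equal variances, a social-only effect and a correlation that the documents do not give. Such a figure would also concern detection of a mean shift, whereas Aim 2 is a regression.

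The reply does not close the gap. Per-block scoring yields two totals, with no rule for which enters the regression or how they are compared, and a social-block total still contains general learning.

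A second reply is that treatment order is randomised, so practice is not aligned with OT. That is right for the average OT effect. It does not protect an association between two change scores that both depend on order, as step 4 of the working shows.

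A third reply is that a difference score can be noisier. This also stands, and it is counted as a cost of the fix.

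**Conclusion.** The point holds as an incomplete definition, together with a missing adjustment. The bandit measure does not say whether it is per block or pooled, no social-versus-nonsocial score is defined for the task, and C.1.h neither names the score nor allows for visit order. It does not hold as a finding that the plan sums the two blocks.

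No numerical size should be attached. The correlations in step 2 apply only if the blocks are pooled, and they rest on assumed SD ratios and correlations. The order bias depends on visit shifts that the documents do not report, and it needs a shift in both the bandit score and the physiological measure. The argument for a contrast is that it matches the construct; a gain in precision is not assured.

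Severity is low. Aim 2 is exploratory, the bandit task is one of its two outcome measures, and the Go/No Go decision is unaffected.

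**What to change.** In C.1.g, define the Aim 2 bandit outcome as optimal choices in the social block minus optimal choices in the nonsocial block, taken as OT minus placebo. The social-block change adjusted for the nonsocial-block change is an acceptable alternative. Choose one before the data are examined. Keep the total, with its block rule stated, as a check on general learning.

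In C.1.h, name that score as the outcome and add a term for visit order (OT first or second) to the Aim 2 regression.

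The change takes a few sentences and needs no new data, since the task already runs the two reward types as separate blocks. It uses one degree of freedom for order. The difference is noisier than the social-block score alone if the block change scores correlate below about 0.5, assuming equal variances. The adjusted version avoids that loss but removes general learning less completely.
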